4. STUDY DESIGN

4.1. GENERAL DESCRIPTION

This is a multicenter, double-blind, randomized, parallel-group phase 3 study in patients with type 1 diabetes mellitus (T1DM) comparing the efficacy, immunogenicity and safety of MYL-1501D products from two manufacturing processes (Process V and Process VI). A total of 202 patients with T1DM are planned to be randomized in a 1:1 ratio between MYL-1501D Process V and MYL-1501D Process VI. Approximately 110 sites will be included in the study.

After up to 2-week screening period, all patients will be titrated on Lantus® during a 4-week run-in period, and will be shifted from their current mealtime insulin to Humalog®. The patients will be randomized (stratified by investigational site and time of administration of glargine [morning and evening]); one group will receive MYL-1501D product from Process V, while the other group will receive MYL-1501D product from Process VI for 18 weeks. A follow-up visit will be scheduled 2 weeks after last dose of MYL-1501D.

The none hypothesis is that the upper bound of treatment difference (Process VI minus Process V) is over 0.4 and alternative hypothesis is that upper bound of treatment difference is less than or equal to 0.4.

Patients will remain blinded until the database is locked, then an unblinding request form will be sent to the IVR provider in order to get the randomization code. Any analyses done prior to database lock will use dummy treatments.

Document: \sasdata\Mylan\Insulin_glargine\SYA22825\Biostatistics\Documentation\SAP\MYL-1501D-3004_SAP_Final_2_0_clean.doc

Author: [name]

Version Number:

2.0

Version Date:

18OCT2018

Template No: CS_TP_BS016 Revision 4
Effective Date: 01Apr2016

Reference: CS_WI_BS005

Analysis Plan Template

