16.2.4. SUBGROUP ANALYSIS

The effect of subgroups mentioned in [section 8.6](#) on the change from baseline HbA1c at week 18 will be examined by employing a MMRM model. The subgroups will be included in the model along with the treatment group. Additionally separate subgroup analysis within each subgroup mentioned in [section 8.6](#) will be performed same MMRM model for treatment comparison within each subgroups.

The similar subgroups will also be examined for the immunogenicity parameters for the percent binding and the incidence analysis of cross reactive antibody. Besides examine subgroup by treatment interaction for percent binding. Separate analysis for both percent binding and incidence will be performed for treatment comparison within each subgroup.

Document:	\sasdata\Mylan\Insulin_glargine\SYA22825\Biostatistics\Documentation\SAP\MYL-1501D-3004_SAP_Final_2_0_clean.doc		
Author:	[name]	Version Number:	2.0
		Version Date:	18OCT2018
Template No:	CS_TP_BS016 Revision 4	Reference:	CS_WI_BS005
Effective Date:	01Apr2016		

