18.1.1. ALL TEAEs

Incidence of TEAEs will be presented by System Organ Class (SOC) and Preferred Term (PT) and also broken down further by maximum severity and relationship to study medication. The number of events will also be presented.

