18.1.5. LOCAL OR SYSTEMIC ALLERGIC REACTION

The local and systemic allergic reactions are recorded on the adverse events page of the eCRF.

TEAE incidence of both local and systemic allergic reaction will be summarized by SOC and treatment group. A separate listing will also be produced which include only events of local or systemic allergic reaction.

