18.6. OTHER SAFETY ASSESSMENTS

18.6.1. IMMUNOGENICITY PROFILES ANALYSES

The following parameter will be summarized for immunogenicity:

- 1) Total Insulin Antibodies
 - Percent Binding (% B/T)
 - Positive/Negative
- 2) Cross Reactive Insulin Antibodies
 - Percent Binding (% B/T)
 - Positive/Negative
- 3) Insulin (Drug), Specific Antibodies
 - Percent Binding (% B/T)

Descriptive statistics will be tabulated by treatment and by timepoint for the continuous variables. Change from baseline to post-baseline timepoints will also be presented. The same MMRM model as the primary efficacy analysis (without imputing missing data and excluding the basal insulin dosing time) will be used. Estimates of the means, LSM means (SE and 2-sided 95% CIs) as well as treatment difference at each visit will be presented. Analyses will be done on the Safety Population.

The dichotomous outcomes will be summarized with frequency and percentage at scheduled visits. Treatment comparison will be performed using Fisher's exact test. P-value for the two-sided test will be presented.

Potential immunogenicity effect on local and systematic allergic reaction, hypersensitivity, and severe hypoglycaemia will be explored by summarizing those incidences between the treatment groups among subjects with post-baseline positive response of cross reactive antibodies. The local and system allergic reactions as well as the hypoglycaemia are found directly on the CRF, the hypersensitivity events will be found in the coded adverse events with the following specifications:

- System Organ Class (SOC): Immune system disorders
- High Level Group Term (HLGT): Allergic conditions
- High Level Term (HLT): Allergies to foods, food additives, drugs and other
- Preferred Term (PT): Drug hypersensitivity
- Lower level term (LLT): Drug hypersensitivity

Document: \sasdata\Mylan\Insulin_glargine\SYA22825\Biostatistics\Documentation\SAP\MYL-1501D-3004_SAP_Final_2_0_clean.doc

Author: [name]

Version Number: 2.0

Version Date:

18OCT2018

Template No: CS_TP_BS016 Revision 4
Effective Date: 01Apr2016

Reference: CS_WI_BS005

Analysis Plan Template

The possible insulin neutralization effect will also be explored by presenting:

- The incidence of patients with increase over 10% in cross reacting antibody from baseline at any visit
- The incidence of patients with increases of HbA1c over 0.2% increase from baseline at any visit

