In addition, nocturnal hypoglycemia rate and incidence will be analyzed in a same way as overall hypoglycemic episodes.

Listings of hypoglycemic episodes and severe hypoglycemic episodes will be presented by visit for each patient. If a sufficient number of severe hypoglycemic episodes are reported, then incidence summaries similar to the incidence of hypoglycemic episodes will be included.

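### The antibody–safety exploration in SAP 18.6.1 tabulates events only among antibody-positive subjects, so the display gives no antibody-negative reference for the question it poses

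*SAP*

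**What the plan says.** SAP V2.0 section 18.6.1 states the aim: "Potential immunogenicity effect on local and systematic allergic reaction, hypersensitivity, and severe hypoglycaemia will be explored". The method completes the same sentence: the effect is to be "explored by summarizing those incidences between the treatment groups among subjects with post-baseline positive response of cross reactive antibodies". Antibody status itself is determined and reported, since "The dichotomous outcomes will be summarized with frequency and percentage at scheduled visits", with a Fisher's exact comparison of the arms. That summary is not crossed with clinical events.

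The same events appear elsewhere without antibody status:

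- **Allergic reactions (18.1.5):** "TEAE incidence of both local and systemic allergic reaction will be summarized by SOC and treatment group", plus a separate listing.
- **Hypersensitivity:** identified in 18.6.1 through the coded preferred term, so it also appears in the general table of treatment-emergent events (18.1.1).
- **Severe hypoglycemia (18.6.2):** listed by patient, and "If a sufficient number of severe hypoglycemic episodes are reported, then incidence summaries similar to the incidence of hypoglycemic episodes will be included".

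In the subgroup section (16.2.4) the antibody result is the outcome and demographic group is the factor: "The similar subgroups will also be examined for the immunogenicity parameters for the percent binding and the incidence analysis of cross reactive antibody". Section 7.3 of protocol V2.0 adds no analysis of events by antibody status.

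**The concern.** The exposure of interest is antibody status, and the method fixes it at positive. The contrast that remains, Process VI against Process V, answers a different question: whether reactions among positives differ by process. It is also made among subjects selected by a response that occurs after randomization. If one process is more immunogenic, its positive subset is a differently selected group, and randomization no longer makes the two subsets comparable.

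The trial compares two manufacturing processes of one product, and immunogenicity is the first of its other objectives. This is the only analysis in the SAP that links antibodies to these events.

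Timing adds some weight. Under 5.2 the final analyses follow database lock and unblinding. Section 18.6.1 says the immunogenicity data will not be available at that lock and will be analyzed later by the method already specified. An antibody-negative comparator added at that stage would be post hoc, chosen when event counts by arm could already be known.

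**Working it through.** There is no figure in the plan to reproduce. The check has two parts.

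**1. Search for the missing contrast.** Every section of SAP V2.0 that uses antibody status or these events was read, together with section 7 of protocol V2.0.

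| Section | Subjects | Split by arm | Split by antibody status |
|---|---|---|---|
| 18.6.1, antibody–event exploration | Post-baseline positives | Yes | Positives only |
| 18.6.1, positive/negative counts | Safety set | Yes | Yes, but no events |
| 18.1, 18.1.1, adverse events by SOC/PT | Safety set | Yes | No |
| 18.1.3, serious events | Safety set | Yes | No |
| 18.1.5, allergic reactions | Safety set | Yes | No |
| 18.6.2, severe hypoglycemia incidence | Safety set, if enough episodes | Yes | No |
| 16.2.4, subgroups | Demographic subgroups | Yes | Antibody result is the outcome |

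No row gives events in antibody-negative subjects or compares positive with negative.

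**2. Illustration of what the positive-only table leaves open.** Input from the documents: N = 202, 1:1 (SAP 4.1). Assumptions, because the documents give no rates: the share of subjects positive and the event counts. With a events in n₊ positives and b events in n₋ negatives, RR = (a/n₊)/(b/n₋).

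Take 50% positive, so n₊ = n₋ = 101, and a = 6. The planned table pooled over arms shows 6 of 101 in every case below.

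| Events in negatives (b) | RR | Difference, percentage points | Fisher p |
|---|---|---|---|
| 1 | 6.0 | +5.0 | 0.12 |
| 3 | 2.0 | +3.0 | 0.50 |
| 6 | 1.0 | 0.0 | 1.00 |
| 12 | 0.5 | −5.9 | 0.22 |

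Varying the share positive:

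- 30% positive (4 events in 61): RR runs from (4/61)/(1/141) = 9.25 to (4/61)/(17/141) = 0.54.
- 70% positive (8 events in 141): RR runs from (8/141)/(1/61) = 3.46 to (8/141)/(7/61) = 0.49.

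**How much the added rows would deliver.** For 6/101 against 3/101, the approximate 95% half-width is 1.96 × √(0.0594 × 0.9406/101 + 0.0297 × 0.9703/101) = 1.96 × 0.029 ≈ 0.057. The difference is therefore 3.0 ± 5.7 points.

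Approximate power across 30% to 70% positive is 51% to 68% for 10% against 2%, and 18% to 35% for 6% against 2%. For 5% against 1% with 40% positive, Fisher power is about 34% pooled (81 against 121) and 9% within one arm (40 against 61). The contrast becomes estimable but remains imprecise.

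**The case against.** The strongest reply is that the table should not be read alone. Process VI is already compared with Process V in all Safety-set subjects for adverse events generally, serious events and allergic reactions (18.1, 18.1.1, 18.1.3, 18.1.5). Severe hypoglycemia is always a serious adverse event and is entered on the adverse event pages (protocol 6.5.2.2.1 and 6.5.2.2.4). It therefore reaches the serious-event table whether or not the condition in 18.6.2 is met.

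A reader could then subtract positives from all subjects. Take 101 per arm, 40% positive and 5% incidence in positives (40.4 × 0.05 = 2.0 events). All-subject events would be about 2.0 + 60.6 × 0.05 = 5.1 if negatives also have 5%, and about 2.0 + 60.6 × 0.01 = 2.6 if they have 1%. Taken together, the planned outputs would differ. This stands. What it does not supply is a planned display, and the subtracted row would mix antibody-negative with untested subjects.

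Three further points stand:

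- The positive-only table is not empty. Whether positives react more on one process than on the other is a fair descriptive question after a manufacturing change.
- A positive-versus-negative contrast is not randomized either, and an event may precede seroconversion.
- The table templates that SAP section 9 refers to are not among the documents, so a negative row in them cannot be excluded. The SAP text specifies none.

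Two stronger readings are tempting. One is that the safety plan cannot show any antibody effect and compares the processes only in positives; the all-subject tables contradict this. The other is that the sponsor will use this table to declare immunogenicity harmless; no passage says so, and 18.6.1 promises only an exploration.

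**Conclusion.** The point holds as a mismatch between question and method. The display described in 18.6.1 does not contain the antibody-negative reference that its stated question needs, and no other section supplies it directly. On the illustrative assumptions above, one positive-only result is compatible with risk ratios from well above 1 to about one half. Those rates are assumed, and the conclusion does not depend on their values.

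The consequence is limited. The analysis is exploratory, the planned safety comparisons between processes are intact, and the primary non-inferiority conclusion is unaffected. A reader might infer that adding negatives would settle whether antibodies matter clinically. It would not: at this sample size the estimate would be imprecise and only an association. This is a cheap improvement.

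**What to change.** In SAP 18.6.1, replace the positive-only summary with a table of each event type (local allergic reaction, systemic allergic reaction, hypersensitivity, severe hypoglycemia) by post-baseline cross-reactive status: positive, negative, not evaluable. Show it within each arm and pooled, in the Safety set, with denominators and the positive-minus-negative difference with a 95% CI. State that it is descriptive and associational, because antibody status is not randomized and an event may precede seroconversion. For the comparison of processes, refer to the all-subject tables already planned in 18.1, 18.1.1, 18.1.3 and 18.1.5.

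The change needs one sentence and one reshaped table, and no new data. The downside is sparse cells and wide intervals, most of all within an arm. It should be made before treatment is unblinded for the main analysis, so that the comparator is pre-specified.

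### In SAP V2.0 18.6.1 the hypersensitivity category rests on one MedDRA term, so allergic-type events coded to another term and not marked as allergic on the eCRF drop out of the antibody-linked summary

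*SAP*

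**What the plan says.** SAP V2.0 section 18.6.1 sets up an exploratory summary: "Potential immunogenicity effect on local and systematic allergic reaction, hypersensitivity, and severe hypoglycaemia will be explored by summarizing those incidences between the treatment groups". It is restricted to a subset, "among subjects with post-baseline positive response of cross reactive antibodies".

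The outcomes come from two sources:

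- **CRF route.** "The local and system allergic reactions as well as the hypoglycaemia are found directly on the CRF".
- **Coded route.** For the remaining outcome, "the hypersensitivity events will be found in the coded adverse events with the following specifications". Five lines follow, one for each MedDRA level. They start at "System Organ Class (SOC): Immune system disorders", pass through a High Level Group Term and "High Level Term (HLT): Allergies to foods, food additives, drugs and other", and end at "Preferred Term (PT): Drug hypersensitivity" and "Lower level term (LLT): Drug hypersensitivity".

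No other Preferred Term, term list or standardised query is given. The SAP does not say whether the five lines apply jointly, apply as alternatives, or only describe where the term sits in the dictionary. SAP V1.0 has the same chain. V2.0 edited section 18.6.1 to deal with late laboratory data and left the chain as it was.

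Allergic events are also reported elsewhere in SAP V2.0. Section 18.1.5 summarises local and systemic allergic TEAEs by System Organ Class and arm, with a separate listing. Section 18.1.1 tabulates every TEAE by System Organ Class and Preferred Term, and section 18.1.3 does so for serious ones. Protocol V2.0 section 7.3 names local and systemic allergic reactions among the safety measures and has no separate hypersensitivity endpoint.

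**The concern.** An adverse event is coded from what the site reports. If the site writes down a manifestation and not a diagnosis of drug hypersensitivity, the event can be coded to a different term, and a one-term search will not find it.

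In 18.6.1 hypersensitivity stands beside the CRF allergic-reaction items as a separate outcome. It is the one item in that summary that could pick up an allergic-type event that the investigator did not mark as allergic. With a single term it can do so only for events that carry that exact label.

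The trial compares two manufacturing processes, and immunogenicity is the first of the other objectives in SAP section 3.1. Section 18.6.1 is the only place where allergic-type events are tied to antibody response. A nearly empty hypersensitivity row there could reflect the search rule as much as the product.

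**Working it through.** There is no figure in the plan to reproduce and no arithmetic to do: the point concerns an event definition. The check is to follow the stated rule and see where an event ends up.

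**Step 1: what the rule admits.** Consider three readings of the five lines.

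- *Joint filter.* An event must carry both the Preferred Term and the Lower Level Term Drug hypersensitivity. An event with the right Preferred Term but another Lower Level Term fails.
- *Description of one term's location.* The search is still for that single term.
- *Alternatives.* The widest lines decide. The High Level Term line, by its own name, then brings in food and food-additive allergies, and the System Organ Class line is wider still.

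The first two readings give a one-term search. The third gives a broad and unspecific one. Nothing in the SAP says that the broader levels are to be used alone, and ending the chain at the lowest level points to the first or second reading. Because the SAP leaves this open, two programmers could produce different counts.

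**Step 2: where an event ends up.** Take an allergic-type TEAE in a subject who meets the antibody criterion, under the one-term reading.

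| Coded as Drug hypersensitivity? | Marked allergic on eCRF? | Hypersensitivity item, 18.6.1 | Allergic-reaction item, 18.6.1 | Allergic table, 18.1.5 | TEAE table, 18.1.1 |
|---|---|---|---|---|---|
| Yes | Yes | counted | counted | counted | counted |
| Yes | No | counted | absent | absent | counted |
| No | Yes | absent | counted | counted | counted |
| No | No | absent | absent | absent | counted |

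The third row is a classification loss: the event is in the antibody-linked summary, but not as hypersensitivity. The fourth row is the real gap: the event is missing from that summary altogether.

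**Step 3: whether another table fills the gap.** Sections 18.1.1 and 18.1.5 cover the safety population. Neither is restricted to antibody-positive subjects, and 18.1.1 does not group allergic-type terms. A reader could not recover the antibody-linked count from them without going back to subject-level data.

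**Step 4: size.** The count lost is the number of fourth-row events among antibody-positive subjects. The documents give neither the expected number of allergic-type events, nor the share marked on the eCRF, nor the expected number of antibody-positive subjects. The denominator is a subset of the treated subjects and not the 202 planned for randomization. No count or percentage follows.

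**Step 5: timing.** SAP section 4.1 unblinds after database lock. Section 18.6.1 says that the immunogenicity data will not be available at that lock, will be locked later, and will be analysed by the method already specified in the SAP. Adverse-event terms by arm can therefore be known before the antibody-linked summary is run. A definition changed at that stage would be post hoc.

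**The case against.** The strongest reply is that these events are already well covered. The sentence that introduces the term chain first takes local and systemic allergic reactions from the CRF, whatever their coded term, and these are the outcomes that the protocol names. Collection is explicit: the schedule of activities has a row for adverse events that includes local and systemic allergic reactions, marked at every visit from V2 to V15, and the visit sections repeat it. Section 18.1.5 reports them by arm with a dedicated listing, and sections 18.1.1 and 18.1.3 show every TEAE and every serious TEAE under its own Preferred Term. Hypersensitivity is a supplementary item in an exploratory summary to which no decision rule is attached.

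Most of this stands. A reader might infer from the one-term chain that reactions coded as, say, anaphylaxis or urticaria are not counted in this trial. The documents do not support that: such events are in the TEAE tables in every case, and in 18.6.1 itself if marked as allergic. A reader might also try to put a capture rate on the rule. That is unsupported too, because it would need invented event counts and would ignore the CRF route. Which terms particular reactions receive is a matter of the dictionary, which the documents do not reproduce; the point does not depend on it.

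The reply does not deal with the fourth row of the table. Prompting at visits makes an unmarked allergic-type event less likely, but Protocol V2.0 gives no definition of a local or systemic allergic reaction, so the mark rests on the investigator's judgement. A coded search would be a useful second check, and a single term makes it a weak one.

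**Conclusion.** The concern holds in a limited form. The hypersensitivity category in SAP V2.0 18.6.1 rests on one Preferred Term and one Lower Level Term. An allergic-type event coded otherwise is not counted as hypersensitivity. If it was also not marked on the eCRF as a local or systemic allergic reaction, it is absent from the only analysis that ties such events to antibody response.

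This assumes that the five lines are applied as a joint filter or as the location of a single term. If they were applied as alternatives, the fault would be an overly broad category that includes food allergy.

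The size is unknown and cannot be derived from the documents. The primary non-inferiority conclusion, the general TEAE tables and the allergic-reaction tables in 18.1.5 are unaffected. A cheap improvement to an exploratory safety analysis is worth making because the plan allows it to be fixed in advance.

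**What to change.** Before the first unblinding, amend SAP section 18.6.1 as follows:

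1. Replace the five-line chain with a pre-specified, broader set of terms. The standardised MedDRA query for hypersensitivity, narrow scope, in version 20.1 (the version that section 18.1 names for adverse events) is one ready-made choice.
2. Define the hypersensitivity outcome as an event that meets this term set or is marked on the eCRF as a local or systemic allergic reaction. Keep the separate CRF-based items as they are.
3. List the contributing Preferred Terms by arm, so that the reader can see what makes up the count.

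The cost is SAP wording and a term list in programming; no new data are collected. The downside is that some allergic events unrelated to the study insulin will be included. The listing will show them.
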